$\geq 75 \times 10^9 / L$ $50 - 74 \times 10^9 / L$ $35 - 49 \times 10^9 / L$ $25 - 34 \times 10^9 / L$ $< 25 \times 10^9 / L$	Continue at same dose level Continue at same dose level Continue at same dose level Continue at same dose level * Hold dosing  * qualifies as a DLT. If resolved to ≤ grade 2, resume therapy according to the rules of Table 5-6 .	Dose at the Time of the Platelet Decline 
 
 5 mg qd	5 mg b.i.d.	5 mg q.AM / 10 mg q.PM	10 mg b.i.d.	10 mg q.AM / 15 mg q.PM	15 mg b.i.d.	
 
 New Maximum Dose That Must be Instituted 
 
 Continue at same dose level	10 mg b.i.d.†	10mg b.i.d.†	
 
 Continue at same dose level	Continue at same dose level‡	
 
 Continue at same dose	5 mg b.i.d.	5 mg b.i.d.	5 mg b.i.d.	5 mg b.i.d.	
 
 5 mg qd	
 
 Discontinue	Hold dosing	
 
 †Patients from stratum 1 ‡Patients from stratum 2						5 mg qd	5 mg b.i.d.	5 mg q.AM / 10 mg q.PM	10 mg b.i.d.	10 mg q.AM / 15 mg q.PM	15 mg b.i.d.	Continue at same dose level			10 mg b.i.d.†	10mg b.i.d.†	Continue at same dose level			Continue at same dose level‡			Continue at same dose		5 mg b.i.d.	5 mg b.i.d.	5 mg b.i.d.	5 mg b.i.d.	5 mg qd	Discontinue	Hold dosing									
5 mg qd	5 mg b.i.d.	5 mg q.AM / 10 mg q.PM	10 mg b.i.d.	10 mg q.AM / 15 mg q.PM	15 mg b.i.d.																																					
Continue at same dose level			10 mg b.i.d.†	10mg b.i.d.†																																						
Continue at same dose level			Continue at same dose level‡																																							
Continue at same dose		5 mg b.i.d.	5 mg b.i.d.	5 mg b.i.d.	5 mg b.i.d.																																					
5 mg qd	5 mg qd	5 mg qd	5 mg qd	5 mg qd	5 mg qd																																					
Discontinue	Hold dosing																																									
In cases of grade 4 thrombocytopenia, follow-up rules according to Section 5.1.2.9.1 . For dose escalation or dose restart guidelines, see Table 5-5 and Table 5-6 .																																										

**Table 5-5 Dose escalation guidelines and allowed maximum doses for patients who have previously decreased dosing for thrombocytopenia**

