## 7 Safety monitoring and reporting

## 7.1 Adverse events

### 7.1.1 Definitions and reporting

An Adverse Event for the purposes of this protocol is defined as the appearance of (or worsening of any pre-existing) undesirable sign(s), symptom(s), or medical condition(s) that occur after patient's signed informed consent has been obtained. Abnormal laboratory values or test results occurring after informed consent constitute Adverse Events only if they induce clinical signs or symptoms, are considered clinically significant, require therapy (e.g., hematologic abnormality that requires transfusion), or require changes in study medication(s).

Adverse Events that begin or worsen after informed consent should be recorded in the Adverse Events eCRF. Conditions that were already present at the time of informed consent should be recorded in the Medical History eCRF. Adverse Event monitoring should be continued for at least 30 days following the last dose of study treatment. Adverse Events (including lab abnormalities that constitute AEs) should be described using a diagnosis whenever possible, rather than individual underlying signs and symptoms. When a clear diagnosis cannot be identified, each sign or symptom should be reported as a separate Adverse Event.

Adverse Events will be assessed according to the Common Terminology Criteria for Adverse Events (CTCAE) version 4.03. If CTCAE grading does not exist for an Adverse Event, the severity of mild, moderate, severe, and life-threatening, **or** grades 1-4, will be used. CTCAE grade 5 (death) will not be used in this study; rather, information about deaths will be collected through a Death form. The occurrence of Adverse Events should be sought by non-directive questioning of the patient during the screening process after signing informed consent and at each visit during the study. Adverse Events also may be detected when they are volunteered by the patient during the screening process or between visits, or through physical examination, laboratory test, or other assessments. As far as possible, each Adverse Event should be evaluated to determine:

- The severity grade (CTCAE grade 1-4)

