## 7.1.2 Laboratory test abnormalities

### 7.1.2.1 Definitions and reporting

Abnormal laboratory values or test results that constitute adverse events or underlying conditions should not be reported separately in addition to the respective adverse events or underlying diagnosis.

Additionally, laboratory abnormalities that are considered clinically significant due to induction of clinical signs or symptoms, or requiring concomitant therapy (e.g. any hematologic abnormality that requires transfusion or cytokine treatment) or changes in study medication, should be recorded on the Adverse Events eCRF. Whenever possible, a diagnosis, rather than a symptom should be provided (e.g. anemia instead of low hemoglobin). Laboratory abnormalities that meet the criteria for Adverse Events should be followed until they have returned to normal or an adequate explanation of the abnormality is found.

Laboratory abnormalities, that do not meet the criteria of clinical significance, as judged by the Investigator, should not be reported as Adverse Events. A grade 3 or 4 event (severe) as per CTCAE does not automatically indicate a SAE unless it meets the definition of serious as defined below and/or as per Investigator's discretion. Dose modifications described in the [Table 5-4](#) for lab abnormalities should not contribute to designation of a lab parameter abnormality as a SAE.

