### **9.5.2.3 Laboratory abnormalities**

For laboratory tests covered by the Common Terminology Criteria for Adverse Events (CTCAE) version 4.03 ([NCI 2009](#)), the study's biostatistical and reporting team will grade laboratory data accordingly. For laboratory tests covered by CTCAE, a grade 0 will be assigned for all non-missing values not graded as 1 or higher. Grade 5 will not be used.

For laboratory tests where grades are not defined by CTCAE, results will be graded by the low/normal/high classifications based on laboratory normal ranges.

The following by-treatment summaries will be generated separately for hematology and biochemistry laboratory tests:

- frequency table for newly occurring on-treatment grades 3 or 4 (see below for details)
- shift tables using CTCAE grades to compare baseline to the worst on-treatment value
- for laboratory tests where CTCAE grades are not defined, shift tables using the low/normal/high/(low and high) classification to compare baseline to the worst on-treatment value.
- listing of all laboratory data with values flagged to show the corresponding CTCAE grades and the classifications relative to the laboratory normal ranges.

Time to onset of grade 3 or higher SECs will be summarized by dose level.

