Specific safety event categories (SEC) include groups of reported adverse events of high interest as outlined in the product case retrieval sheet. The version of the most up to date document used for the clinical study report will be provided in tables footnotes.

For each specified SEC, number and percentage of patients with at least one event part of the SEC will be reported.

One summary table will be produced for AE to summarize the number (%) of patient from Safety Set:

- who died.
- who died during study treatment and within 30 days after discontinuation of study treatment.
- Who died after 30 days from treatment discontinuation
- reporting AEs regardless of relationship to study treatment.
- reporting AEs with suspected relationship to study treatment.
- reporting SAEs regardless of relationship to study treatment.
- reporting SAEs with suspected relationship to study treatment.

- reporting AEs of CTC grade 3-4 regardless of relationship to study treatment.
- who discontinued from study due to AEs.
- AEs requiring study drug dose adjustment or interruption
- reporting AEs of specific safety event categories. The list of categories will be based on the latest version of case retrieval sheet.

The following summaries will be produced for patients in the Safety Set with number (%) of patients:

- reporting AEs, regardless of relationship to study drug, by system organ class and preferred term.
- reporting AEs, regardless of relationship to study drug, by preferred term.
- reporting AEs, for patients who died, by system organ class and preferred term.
- reporting SAEs, regardless of relationship to study drug, by system organ class and preferred term.
- reporting AEs leading to discontinuation, regardless of relationship to study drug, by system organ class and preferred term.
- reporting AEs requiring dose adjustment or study-drug interruption, regardless of relationship to study drug, by system organ class and preferred term.
- reporting specific safety event categories (SEC), regardless of relationship to study drug, by SEC category.
- reporting AEs, with suspected relationship to study drug, by system organ class and preferred term.
- reporting SAEs, with suspected relationship to study drug, by system organ class and preferred term.
- reporting AEs leading to discontinuation, with suspected relationship to study drug, by system organ class and preferred term.

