2.3.3 Laboratory abnormalities

For laboratory tests covered by the Common Terminology Criteria for Adverse Events (CTCAE) version 4.03 ([NCI 2009](#)). A grade 0 will be assigned for all non-missing values not graded as 1 or higher. Grade 5 will not be used. All lab values occurring between the treatment start date and 30 days after the end of the study treatment will be taken into account.

The following by-strata summaries will be generated separately for hematology, coagulation and biochemistry laboratory tests:

- frequency table for newly occurring or worsened on-treatment abnormalities
- shift tables using CTCAE grades to compare baseline to the worst on-treatment value

- for laboratory tests where CTCAE grades are not defined, shift tables using the low/normal/high/(low and high) classification to compare baseline to the worst on-treatment value.
- listing of all laboratory data with values flagged to show the corresponding CTCAE grades and the classifications relative to the laboratory normal ranges.

A summary and a plot will be produced for hemoglobin level and platelet count over time by visit and stratum.

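### From Day 29, whether an asymptomatic low platelet count must be recorded as an adverse event can depend on the current dose, so thrombocytopenia AE and SEC rates by starting-dose group can differ for the same counts

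*Protocol*

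**What the plan says.** **What makes a low count an AE.** Protocol 7.1.1 gives four alternative routes for a laboratory value. The first is clinical signs or symptoms, and the second is that the value is considered clinically significant. The other two are that the values "require therapy (e.g., hematologic abnormality that requires transfusion), or require changes in study medication(s". Section 7.1.2.1 adds: "Laboratory abnormalities, that do not meet the criteria of clinical significance, as judged by the Investigator, should not be reported as Adverse Events". The same section describes clinical significance in terms of symptoms, concomitant therapy or a change in study drug.

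**When a change in study drug is required.** For thrombocytopenia from Day 29 to end of treatment, Table 5-4 is indexed by "Dose at the Time of the Platelet Decline", and its entries stand under "New Maximum Dose That Must be Instituted".

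**How the events are tabulated.** SAP 2.1.1 classifies patients, within stratum, by first dose received: Group 1 is 5/5 or 5/10 mg (morning/evening), Group 2 is 10/10, and Group 3 is 10/15 or 15/15. SAP 2.3.2 states that "Specific safety event categories (SEC) include groups of reported adverse events of high interest". Protocol 9.5.2.3 states that "Time to onset of grade 3 or higher SECs will be summarized by dose level".

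**How the measured counts are tabulated.** The lead-in to SAP 2.3 puts all safety tables by groups of dose levels, and Protocol 9.5.2.3 calls the laboratory summaries by-treatment. SAP 2.3.3 says: "The following by-strata summaries will be generated separately for hematology, coagulation and biochemistry laboratory tests". It also gives the platelet and hemoglobin summaries by visit and stratum. SAP 2.2.1 and 2.2.2, by contrast, name both stratum and group.

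**The concern.** A patient with a platelet count of 40 x10^9/L, no symptoms and no transfusion has a required dose change on 10 mg b.i.d. but not on 5 mg b.i.d. The first patient's count is an AE by rule. The second patient's count is an AE only if the investigator considers it clinically significant. The event record then depends on the dose as well as on the count, and the SECs inherit this because they are built from reported AEs.

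The frequency, duration and severity of thrombocytopenia are a named focus of the secondary safety endpoint (Protocol 2.2). A reader of AE or SEC tables by starting-dose group would take a rising rate as a dose-toxicity gradient, and part of it could come from the recording rule. The Stratum 1 contrast of 10 mg b.i.d. with higher starting doses is the sensitive one. It is the setting of Amendment 4, whose rationale reports frequent dose reductions at 15 mg b.i.d. after the first cycle, when the dose-dependent rows apply. The rationale does not give the reasons for those reductions.

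**Working it through.** The plan states no figure on this point, so there is none to reproduce. The check codes Table 5-4 and asks what happens when every group has the same platelet counts.

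**Step 1. Is a dose change required from Day 29?** (source: Table 5-4)

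| Count (x10^9/L) | 5/5 | 5/10 | 10/10 | 10/15 | 15/15 |
|---|---|---|---|---|---|
| >=75 | no | no | no | no | no |
| 50-74, Stratum 1 (as read) | no | no | no | yes | yes |
| 50-74, Stratum 2 (as read) | no | no | no | no | no |
| 35-49 | no | yes | yes | yes | yes |
| 25-34 | yes | yes | yes | yes | yes |
| <25 | yes | yes | yes | yes | yes |

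Placing the Stratum 1 reduction in the 50-74 band is a reading of a table broken in extraction. The 35-49 row does not depend on it. Only those two rows separate starting doses.

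On Days 1-28, treatment-related thrombocytopenia follows one rule at every dose: continue unless the count is below 25, then hold.

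**Step 2. Formula.** Let p(b) be the share of patients whose lowest count falls in band b, the same in every group. Let f be 1 if a change is required and 0 otherwise. Let q be the probability that a count with no required change is still recorded as clinically significant. Then

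AE rate = sum over bands below 75 of p(b) x [f + (1 - f) x q].

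Take half of Group 1 on 5/5 and half on 5/10, with everyone still on the starting dose. The gaps reduce to:

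- Group 3 minus Group 2, Stratum 1: p(50-74) x (1 - q)
- Group 2 minus Group 1, either stratum: 0.5 x p(35-49) x (1 - q)

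**Step 3. Numbers.** The documents give neither p(b) nor q. Three assumed distributions, as shares for >=75 / 50-74 / 35-49 / 25-34 / <25:

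- A: 30/40/15/10/5%
- B: 10/35/30/15/10%
- C: 5/20/35/25/15%

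Stratum 1 AE rates for Groups 1/2/3:

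| | q = 0 | q = 0.5 | q = 1 |
|---|---|---|---|
| A | 22.5/30/70% | 46.25/50/70% | 70/70/70% |
| B | 40/55/90% | 65/72.5/90% | 90/90/90% |
| C | 57.5/75/95% | 76.25/85/95% | 95/95/95% |

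Example, B at q = 0: Group 2 = 30 + 15 + 10 = 55%. Group 3 = 35 + 55 = 90%. Group 1 is the mean of 25% (5/5) and 55% (5/10) = 40%.

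At q = 0 the Group 3 minus Group 2 gap is 40, 35 and 20 points, and the Group 2 minus Group 1 gap is 7.5, 15 and 17.5 points. At q = 0.5 each is halved. At q = 1 each is zero.

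**Step 4. Grade >=3 time to onset.** Protocol 3.4.5 associates grade 1 or 2 platelet decline with counts of 50-100 x10^9/L. On that basis the 50-74 band lies below grade 3. The time-to-onset summary is then exposed only through the 35-49 row, which separates 5/5 from all other starting doses.

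**The case against.** The strongest reply is that count-based tables by dose are already planned. The SAP 2.3 lead-in puts every safety table by dose group, SAP 2.1.1 analyses patients by stratum and then by first dose, and Protocol 9.5.2.3 calls the laboratory summaries by-treatment. By-strata in SAP 2.3.3 may therefore add stratum to the dose grouping and not replace it. This largely stands: a reader might infer that the plan has no count-based view by dose, and the documents do not support that. What remains is that SAP 2.3.3 names strata alone, the only time to onset named is SEC-based, and neither document says which source governs dose-group statements on thrombocytopenia.

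A second reply is that clinical significance is a separate, dose-neutral route to an AE. It stands on the wording of 7.1.1, and it is why the gap can be zero. Section 7.1.2.1 weakens it by describing clinical significance partly through changes in study drug, so how investigators apply it is uncertain.

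A third is dilution, which also stands. Table 5-4 works on the dose at the time of decline, while the tables use the starting dose. Escalation is allowed after Day 56 (Protocol 5.1.2.7), and Group 1 pools doses on opposite sides of the 35-49 rule.

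A reader might also cite the 25-34 row, where 5 mg qd continues. That dose is level (-1), not a starting dose, and all five starting doses require a change in that band.

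**Conclusion.** The point holds in limited form. From Day 29 the recording of asymptomatic low counts as AEs can depend on current dose, and any resulting bias runs towards more AEs and SECs at higher doses. It arises in the 35-49 band in both strata, and in Stratum 1 in a higher band if the broken row is read as 50-74.

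The size cannot be derived from the documents. The illustration gives 20-40 points between Stratum 1 Groups 3 and 2, and 7.5-17.5 points between Groups 2 and 1, when nothing beyond the required changes is recorded. Both fall to zero when every low count is recorded. These figures rest on assumed nadirs, an even split of Group 1 and no prior dose change.

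Two stronger readings are not supported. A reader might infer that the rates must differ for equal counts; they can, but the clinical-significance route may close the gap. A reader might also infer that the MSSD or the Amendment 4 decision was biased. DLTs are confined to the first 28 days and their platelet criterion is a count (Table 5-3), so they are unaffected. Amendment 4 cites dose reductions and clinical benefit, not AE rates. What is exposed is the descriptive reading of the thrombocytopenia AE and SEC tables across dose groups. The correction is cheap and worth making.

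**What to change.** 1. In SAP 2.3.3, state that the CTCAE-graded hematology tables (newly occurring or worsened grade, shift to worst grade) and the platelet summaries over time are shown by stratum and starting-dose group. This reconciles the section with the SAP 2.3 lead-in and Protocol 9.5.2.3.
2. Derive time to first grade >=3 thrombocytopenia from laboratory counts and present it alongside the SEC-based version.
3. State that dose-group statements on thrombocytopenia rest on the count-based results.
4. Keep the thrombocytopenia AE and SEC rows, with a footnote that recording of asymptomatic counts could depend on the dose being taken.

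The cost is SAP wording and a little re-programming of data already collected. Laboratory-based rates may be higher than AE-based rates in the low-dose groups, which the footnote explains. No dosing rule changes.

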## 7.1.2 Laboratory test abnormalities

### 7.1.2.1 Definitions and reporting

Abnormal laboratory values or test results that constitute adverse events or underlying conditions should not be reported separately in addition to the respective adverse events or underlying diagnosis.

Additionally, laboratory abnormalities that are considered clinically significant due to induction of clinical signs or symptoms, or requiring concomitant therapy (e.g. any hematologic abnormality that requires transfusion or cytokine treatment) or changes in study medication, should be recorded on the Adverse Events eCRF. Whenever possible, a diagnosis, rather than a symptom should be provided (e.g. anemia instead of low hemoglobin). Laboratory abnormalities that meet the criteria for Adverse Events should be followed until they have returned to normal or an adequate explanation of the abnormality is found.

Laboratory abnormalities, that do not meet the criteria of clinical significance, as judged by the Investigator, should not be reported as Adverse Events. A grade 3 or 4 event (severe) as per CTCAE does not automatically indicate a SAE unless it meets the definition of serious as defined below and/or as per Investigator's discretion. Dose modifications described in the [Table 5-4](#) for lab abnormalities should not contribute to designation of a lab parameter abnormality as a SAE.

## 7.2 Serious adverse events

### 7.2.1 Definitions

Serious adverse event (SAE) is defined as one of the following:

- Is fatal or life-threatening
- Results in persistent or significant disability/incapacity
- Constitutes a congenital anomaly/birth defect
- Is medically significant, i.e., defined as an event that jeopardizes the patient or may require medical or surgical intervention to prevent one of the outcomes listed above
- Requires inpatient hospitalization or prolongation of existing hospitalization, unless hospitalization is for:
  - Routine treatment or monitoring of MF, not associated with any deterioration in condition
  - Elective or pre-planned treatment for a pre-existing condition that is unrelated to the indication under study and has not worsened since signing the informed consent
  - Treatment on an emergency outpatient basis for an event not fulfilling any of the definitions of a SAE given above and not resulting in hospital admission
  - Social reasons and respite care in the absence of any deterioration in the patient's general condition
  - Any SAEs that are expected due to MF, including if the SAE is a primary outcome measure, and whether there has been a clear agreement with regulators not to consider these as SAEs, provided the information is collected elsewhere

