## 1 Background

### 1.1 Overview of myelofibrosis and current treatment options

The four classic myeloproliferative neoplasms (MPNs) include chronic myelogenous leukemia (CML), polycythemia vera (PV), essential thrombocythemia (ET) and primary myelofibrosis (PMF). Myelofibrosis (MF) can present as a de novo disorder (PMF) or evolve secondarily from previous PV or ET (post-PV-MF or post ET-MF). Regardless of whether MF is a primary or secondary disorder, it is characterized by a clonal stem cell proliferation associated with production of elevated serum levels of multiple inflammatory and proangiogenic cytokines, a characteristic bone marrow stromal pattern that includes varying degrees of collagen fibrosis, osteosclerosis and angiogenesis and a peripheral blood smear showing a leukoerythroblastic pattern with varying degrees of circulating progenitor cells. Clinically, MF is characterized by progressive anemia, leukopenia or leukocytosis, thrombocytopenia or thrombocythemia and multi-organ extramedullary hematopoiesis most prominently involving the liver and spleen. Patients may experience severe constitutional symptoms, sequelae of massive splenomegaly (pain, limitations of movement, early satiety and shortness of breath, hepatic obstruction, and splenic infarction), a hypermetabolic state with cachexia, progressive hematopoietic failure, progression to leukemia, and premature death.

The median age at diagnosis is approximately 60 to 65 years. The incidence of PMF has been estimated at 1.5 cases per 100,000 people. Survival in MF varies with the presence or absence of specific risk factors. ([Cervantes et al 2009](#)) have recently published a multi-center analysis of risk factors and their impact on prognosis in patients with MF. They identified age of greater than 65 years, presence of constitutional symptoms (weight loss > 10% of the baseline value in the year preceding PMF diagnosis, unexplained fever, or excessive night sweats persisting for more than 1 month), anemia (Hgb less than 10 g/dL), leukocytosis (white blood cell count (WBC) greater than  $25 \times 10^9/L$ ), and a circulating blast percentage of 1% or higher as individually predictive of outcome. They demonstrated that patients could be distinctly grouped into four categories without overlapping median survival curves based upon their number of risk factors ([Table 1-1](#)).

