### 2.2 Study endpoints

#### Primary

- Incidence rate of Dose Limiting Toxicities (DLT)

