#### Secondary

- Safety will be assessed by monitoring the frequency, duration and severity of adverse events and serious adverse events with a focus on hemorrhagic events, thrombocytopenia, neutropenia, anemia, blood cell component transfusions, or grade 3 or 4 non-hematologic toxicities.
- Plasma INC424 concentration
- Platelets, cytokines and palpable spleen length over time
- Proportion of patients achieving ≥ 50% reduction in palpable spleen length at Week 24 (Study Day 168) relative to Study Day 1

- Change in spleen length as measured by palpation from Study Day 1 to each visit where the variable is measured

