### **7.2.2 Reporting**

To ensure patient safety, every SAE, **regardless of suspected causality**, occurring after the patient has provided informed consent and until at least 30 days after the patient has stopped study treatment must be reported to the Sponsors or designee within 24 hours of learning of its occurrence. Any SAEs experienced after this 30-day period should only be reported to the Sponsors or designee if the Investigator suspects a causal relationship to the study drug. Recurrent episodes, complications, or progression of the initial SAE must be reported as follow-up to the original episode within 24 hours of the Investigator receiving the follow-up information. A SAE occurring at a different time interval or otherwise considered completely unrelated to a previously reported one should be reported separately as a new event.

Information about all SAEs is collected and recorded on the Serious Adverse Event Report Form. The investigator must assess and record the relationship of each SAE to the study drug, complete the SAE Report Form in English, and send the completed, signed form by fax within 24 hours to the Sponsors' Integrated Medical Safety (IMS) department.

The telephone and telefax number of the contact persons in the local department of Integrated Medical Safety (IMS), specific to the site, are listed in the investigator folder provided to each site. The original copy of the SAE Report Form and the fax confirmation sheet must be kept with the case report form documentation at the study site.

Follow-up information is sent to the same person to whom the original SAE Report Form was sent, using a new SAE Report Form stating that this is a follow-up to the previously reported SAE and giving the date of the original report. Each re-occurrence, complication, or progression of the original event should be reported as a follow-up to that event regardless of when it occurs. The follow-up information should describe whether the event has resolved or continues, if and how it was treated and whether the patient continued or withdrew from study participation.

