#### **7.5 Data Monitoring Committee**

Not applicable.

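### The last hospitalisation exception in the SAE definition could let some cytopenia admissions attributed to myelofibrosis miss 24-hour reporting and the SAE counts

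*Protocol*

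**What the plan says.** Protocol section 7.2.1 gives five criteria that make an event serious: fatal or life-threatening, disabling, a birth defect, medically significant, and hospitalisation. Only the last has exceptions. It is introduced by "Requires inpatient hospitalization or prolongation of existing hospitalization, unless hospitalization is for" and five bullets follow. The fifth covers "Any SAEs that are expected due to MF, including if the SAE is a primary outcome measure" and continues, after the word and, with "whether there has been a clear agreement with regulators not to consider these as SAEs, provided the information is collected elsewhere".

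Four other parts of the protocol bear on how that bullet works.

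- The sole primary endpoint (section 2.2) is the incidence of DLTs. Table 5-3 defines these as treatment-related events through Study Day 28. They include a platelet count below 25 x 10^9/L, thrombocytopenia needing platelet transfusion, grade 4 neutropenia, febrile neutropenia and hemorrhage of grade 2 or more.
- Section 1.1 describes myelofibrosis clinically by "progressive anemia, leukopenia or leukocytosis, thrombocytopenia or thrombocythemia", among other features.
- The secondary safety endpoint (section 2.2) counts adverse events and "serious adverse events with a focus on hemorrhagic events, thrombocytopenia, neutropenia, anemia, blood cell component transfusions".
- Section 7.2.2 says that every SAE, whatever its suspected cause, from consent "until at least 30 days after the patient has stopped study treatment must be reported to the Sponsors or designee within 24 hours".

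SAP section 2.3.2 tabulates SAEs both overall and with suspected relationship to study drug. On a data monitoring committee, protocol section 7.5 says "Not applicable".

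**The concern.** An exception of this kind suits a trial whose primary outcome is a clinical event of the disease that is counted elsewhere. Here the primary outcome is toxicity, and the main toxicity resembles the disease. Deciding whether a low count is due to the drug or to marrow failure is hard in a single-arm, open-label study, yet the bullet lets that judgement settle whether an admission is serious at all.

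Two things are at stake. The first is speed: an exempted admission goes on the AE eCRF but carries no 24-hour notice. The second is the SAE tables by stratum and dose group. These could be low for the event types that the secondary endpoint singles out, by an amount that depends on how each site reads the bullet.

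**Working it through.** The plan gives no figure to reproduce, so the check is textual.

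**What must be true for an event to escape.** Reading section 7.2.1 literally, an event leaves SAE status through the last bullet only if all of these hold:

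1. Hospitalisation is the only seriousness criterion it meets.
2. It is judged to be expected from myelofibrosis.
3. A regulator agreement exists, if that clause is read as a condition.
4. The information is collected elsewhere.

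**How much each condition protects.**

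- *Condition 1.* This is a real limit. However, the medically significant criterion refers to preventing the outcomes listed before it (death or threat to life, disability, birth defect), or to jeopardy to the patient. An admission to transfuse a stable patient need not meet it. Section 7.1.2.1 adds that grade 3 or 4 alone does not make an event an SAE, and that dose modifications for laboratory abnormalities should not count towards that status. Hospitalisation is therefore an important route to seriousness for cytopenias.
- *Condition 2.* No list of expected events is given, so the site decides.
- *Condition 3.* The clause is introduced by and whether, which does not state a condition that a site can apply. The documents record no agreement.
- *Condition 4.* This is easily met. Section 7.1.1 already has hospitalisation recorded on the AE eCRF as an action taken.

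**Which event types fit condition 2.** Section 1.1 set against Table 5-3 and the secondary endpoint:

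| Event type | Named as a feature of MF in section 1.1 | DLT criterion | Named in the secondary endpoint |
|---|---|---|---|
| Thrombocytopenia | Yes | Yes | Yes |
| Anemia | Yes | No | Yes |
| Neutropenia | Only as leukopenia | Yes (grade 4) | Yes |
| Febrile neutropenia | No | Yes | Not by name |
| Hemorrhage | No | Yes (grade 2 or more) | Yes |

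The exposure is mainly to thrombocytopenia and anemia, with neutropenia less direct. Hemorrhage fits poorly: section 1.1 does not name it in its clinical description, and exclusion criteria 5 and 6 keep out bleeding-prone patients.

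**What the bullet adds to the other exceptions.** The first exception already removes routine treatment or monitoring of myelofibrosis without deterioration. What remains for the last bullet is mainly disease-type admissions with deterioration.

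**Whether separate DLT capture fills the gap.** SAP section 2.3.2 lists and summarises DLTs, but only treatment-related events in the first 28 days. Planned treatment is 156 weeks, or 156 x 7 = 1,092 days, so the DLT window is 28 / 1,092 = 2.6% of it. In the earlier phase I/II study, section 1.2.4 reports that 20% of grade 3 or higher thrombocytopenia events fell in the first 4 weeks, so 100 - 20 = 80% came later. Those patients entered with platelets of at least 100 x 10^9/L and the figure is not about admissions. It shows only that later events are not a marginal class. Anemia has no DLT listing at any time.

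**The case against.** The strongest reply is that the exempt events are those expected from the disease, while DLTs must be treatment-related, so the two sets should not meet. The mention of a primary outcome measure qualifies the first set and does not add a second. This stands against the stronger reading that a reader might take from the bullet, namely that it exempts the DLT events themselves. A toxicity judged drug-related, whether a bilirubin rise, a bleed or a cytopenia, is not an event expected from myelofibrosis, and the DLT criteria as a group do not fall under the exception. The reply does not dispose of the point, because the same low count can be attributed either way and the bullet acts after that attribution.

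A second reply is that no regulator agreement is shown, so the exception is not available. That is a fair reading, but the wording does not force it on a site.

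Third, there is no contradiction with section 7.2.2, which governs events already classed as SAEs. That is correct. What exists is a tension: reporting is meant to be independent of cause, while the definition lets cause back in.

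Fourth, dose decisions do not depend on SAE forms. Section 5.1.2.3 brings all clinical, laboratory and non-DLT adverse event data to the escalation meeting. Section 5.1.2.8 requires review of all adverse events before escalation, and consultation with the Sponsors before treatment resumes after a DLT. The SAP also tabulates grade 3-4 events, events needing dose adjustment or interruption, safety event categories and laboratory grades, whatever their seriousness. This stands, so it would be wrong to infer that toxicity goes unseen. These routes carry no 24-hour limit, however, and they do not restore the SAE counts.

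**Conclusion.** The last exception is defective as written. It could remove from expedited reporting and from the SAE tables some admissions, mainly cytopenias including anemia and events after Day 28, that a site attributes to myelofibrosis and that are serious by hospitalisation alone. It is worth correcting because the stated rule can itself drop events that a named secondary endpoint is meant to count.

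The size cannot be estimated. The documents give no admission rate, no share of admissions that are serious by hospitalisation alone, and no record of how sites read the bullet. The 26% with grade 3 or 4 platelet declines in section 1.2.4 is a laboratory rate from another study and cannot be turned into a count of missed SAEs. The number may be zero.

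The conclusion assumes that at least one site does not treat the regulator clause as a binding condition, and that some cytopenia admissions meet no other seriousness criterion. The primary DLT analysis is not affected, and events that are fatal, life-threatening, disabling or medically significant remain SAEs.

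**What to change.** Delete the last bullet of the hospitalisation exceptions in protocol section 7.2.1. If the sponsor wants to keep it:

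- limit it to progression of myelofibrosis itself, which section 7.1.1 already keeps out of adverse event reporting unless a separate event accompanies it;
- state the regulator agreement, the exempt events and where they are collected;
- say that it never applies to treatment-related events, events meeting a DLT criterion, hemorrhagic events or cytopenias.

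Before the final SAE tables, query AE records in which hospitalisation is recorded but the event is marked non-serious, and correct them where needed.

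The cost is one amended bullet, one reconciliation query on data already in the AE eCRF, and a few more SAE forms.
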